#### **5.5 Efficacy Endpoints**

The primary endpoints of this study are safety, tolerability, and efficacy (anti-tumor activity) that will be obtained at completion of the study. The study will provide additional data regarding safety, anti-tumor activity and efficacy of the combinations and will suggest possible biomarkers of response.

The plan is to evaluate the overall response rate (ORR), progression free survival (PFS), and duration of response (DOR) of the study population receiving the combinations of pembrolizumab and pralatrexate (Arm A), pralatrexate, decitabine and pembrolizumab (Arm B), and decitabine and pembrolizumab (Arm C).

#### **5.6 Biomarker Research**

The trial will aim to identify biomarkers that may correlate with clinical activity of pembrolizumab through the following steps:

- Analyze the changes on T cell repertoire in peripheral blood and primary tumor samples as a function of treatment with pralatrexate, decitabine and pembrolizumab and assess the contribution of epigenetic priming with decitabine in patients receiving treatment with pembrolizumab and pralatrexate.

Standard flow cytometry to assess CD3, CD4, CD8, CD25, CD80, PD1, PD-L1, PD-L2 and Foxp3 will be performed in peripheral blood mononuclear cells. In addition, peripheral blood T lymphocytes will be analyzed by flow cytometry for CD45 RA, CCR7, CD62L to understand changes in the T cell repertoire. Correlation in between changes and response to treatment will be made.

Paraffin embedded primary tumor samples will be obtained pre- and post-treatment as defined below and OpalMultiplexing “MANTRA” will be performed. MANTRA is a tissue evaluation technique, which uses a fluorescent signal amplification probe to permit serial immunohistochemistry and compared to conventional immunohistochemistry permits multiplex detection. Opal Multiplexing MANTRA will be used to determine changes in the microenvironment (TILs, NK-cell and antigen-presenting cells) as a function of treatment. The following set of 6 markers will be analyzed on each tissue biopsy: CD3, CD7, CD4, CD8, PGM1, IDO; CD3, CD7, CD4, CD8, CD20, FOXP3; CD3, CD7, CD4, CD8, PD-1, PD-L1; CD3, CD7, CD4, CD8, CD56, Granzyme B.

- Elucidate the immune modulatory effect of pralatrexate and decitabine and identify biomarker of response accounting for heterogeneity and dynamic changes.

Gene expression profiling (GEP) analysis will be obtained on primary tumor samples pre- and post-treatment. Changes of gene expression profiling as a function of treatment with pralatrexate and decitabine will be analyzed. Specific attention will be placed on defined gene-signature already described and predictive of response to pembrolizumab (e.g. interferon- $\gamma$ -related genes including CXCL9, CXCL10, IDO1, IFNG, HLA-DRA, STAT1). Additional signature associated with clinical outcome will be investigated.

Genome wide methylation analysis will be performed to identify and quantify changes in methylation pre- and post-treatment. Specific attention will be placed on decitabine contribution in de-repressing and inducing transcription of multiple DNA hypermethylated human endogenous retrovirus (HERV) genes triggering a type I interferon-response.

GEP and methylation wide methylation profiling will be analyzed, and correlation will be made to identify biomarkers of response. The data gathered from the GEP and genome wide methylation will be used to create an algorithm of regulatory networks within PTCLs. The analysis of these data will provide information on etiology of PTCLs and will suggest possible targetable oncogenic pathways.

## 6.0 METHODOLOGY

### 6.1 Diagnosis/Condition for Entry into the Trial

Patients must have histologically confirmed diagnosis of relapsed and refractory (R/R) peripheral T-cell lymphoma (PTCL) or cutaneous T-cell lymphoma (CTCL).

#### 6.1.1 Subject Inclusion Criteria

In order to be eligible for participation in this trial, the subject must:

1. Be willing and able to provide written informed consent/assent for the trial.
2. Be  $\geq 18$  years of age on day of signing informed consent.
3. Have measurable disease as defined by the Lugano Criteria for PTCL (Cheson et al., 2014) and by the Global Response Score for CTCL (Olsen et al., 2011).
4. Patient must have histologically confirmed relapsed or refractory Peripheral T-cell lymphoma (PTCL) or cutaneous T-cell Lymphoma (CTCL) as per WHO criteria and TNMB classification and staging.
5. There is no upper limit for the number of prior therapies. Patient may have relapsed after prior autologous stem cell transplant.
6. Patients who had prior treatment for their disease, as long as there is radiographic evidence of refractory or relapsed disease and the patient meets all other clinical and laboratory criteria for study treatment.
7. Be willing to provide tissue from a newly obtained core or excisional biopsy of a tumor lesion. Be willing to provide FNA of a tumor lesion. *Newly-obtained is defined as a specimen obtained up to 6 weeks (42 days) prior to initiation of treatment on Day 1. Subjects for whom newly obtained samples cannot be provided (e.g. inaccessible or subject safety concern) may submit an archived specimen only upon agreement from the Sponsor.*
8. Have a performance status of 0 or 1 on the ECOG Performance Scale.
9. Demonstrate adequate organ function as defined in Table 6, all screening labs should be performed within 10 days of treatment initiation.

Table 6: Adequate Organ Function Laboratory Values.

System	Laboratory Value
Hematological	
Absolute neutrophil count (ANC)	$\geq 1,000 / \text{mcL}$
Platelets	$\geq 75,000 / \text{mcL}$
Hemoglobin	$\geq 9 \text{ g/dL}$ or $\geq 5.6 \text{ mmol/L}$ without transfusion or EPO dependency (within 7 days of assessment)
Renal	
Serum creatinine OR Measured or calculated a creatinine clearance (GFR can also be used in place of creatinine or CrCl)	$\leq 1.5 \times \text{upper limit of normal (ULN)}$ OR $\geq 60 \text{ mL/min}$ for subject with creatinine levels $> 1.5 \times$ institutional ULN
Hepatic	
Serum total bilirubin	$\leq 1.5 \times \text{ULN}$ OR Direct bilirubin $\leq \text{ULN}$ for subjects with total bilirubin levels $> 1.5 \times \text{ULN}$
AST (SGOT) and ALT (SGPT)	$\leq 2.5 \times \text{ULN}$ OR $\leq 5 \times \text{ULN}$ for subjects with liver metastases
Albumin	$\geq 2.5 \text{ mg/dL}$
Coagulation	
International Normalized Ratio (INR) or Prothrombin Time (PT)	$\leq 1.5 \times \text{ULN}$ unless subject is receiving anticoagulant therapy as long as PT or PTT is within therapeutic range of intended use of anticoagulants
Activated Partial Thromboplastin Time (aPTT)	$\leq 1.5 \times \text{ULN}$ unless subject is receiving anticoagulant therapy as long as PT or PTT is within therapeutic range of intended use of anticoagulants

aCreatinine clearance should be calculated per institutional standard.

10. Female subjects of childbearing potential should have a negative urine or serum pregnancy within 72 hours prior to receiving the first dose of study medication. If the urine test is positive or cannot be confirmed as negative, a serum pregnancy test will be required.

11. Female subjects of childbearing potential (Section 7.7.9.2) must be willing to use an adequate method of contraception as outlined in Section 7.9.2 – Contraception for the course of the study through 120 days after the last dose of study medication.

Note: Abstinence is acceptable if this is the usual lifestyle and preferred contraception for the subject.

12. Male subjects of childbearing potential (Section 7.9.2) must agree to use an adequate method of contraception as outlined in Section 7.9.2- Contraception, starting with the first dose of study therapy through 120 days after the last dose of study therapy.

Note: Abstinence is acceptable if this is the usual lifestyle and preferred contraception for the subject.

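### The albumin limit in Table 6 is printed as at least 2.5 mg/dL, a level so low that the albumin row excludes no one

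*Protocol*

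**What the plan says.** Inclusion criterion 9 (Protocol Section 6.1.1) makes the laboratory table binding: the patient must "Demonstrate adequate organ function as defined in Table 6, all screening labs should be performed within 10 days of treatment initiation". The table is headed "Table 6: Adequate Organ Function Laboratory Values". Its albumin row, in the hepatic block, reads ≥ 2.5 mg/dL. The hemoglobin row of the same table is given in g/dL, with a mmol/L equivalent.

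Albumin reappears in two other relevant places, and neither supplies a limit or a unit. Table 15 (Section 9.1.7) lists it only as a chemistry test. Section 4.3.2 names serum albumin as a contributor to the 67-86% plasma protein binding of pralatrexate. Section 5.4, which sets the blood values needed before each cycle, has no albumin requirement.

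Section 9.1.10 has each site send a completed eligibility checklist and supporting laboratory results to the coordinating center before a patient is enrolled. Exclusion 12 (Section 6.1.2) lets the treating investigator exclude a patient for a laboratory abnormality that might confound the results or make participation against the patient's interest.

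**The concern.** Serum albumin is measured in grams per deciliter, or tens of grams per liter. A limit of 2.5 milligrams per deciliter lies far outside that scale. An eligibility limit that no measured value can fail does no screening, even though it sits in a mandatory criterion.

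Two things are at stake. The first is the entry screen: whatever albumin level the authors meant to exclude is not excluded by the text as approved. The second is consistency. Section 2.1 describes an international, multicenter study. A site that follows the text accepts a patient with albumin of 1.5 g/dL. A site that assumes g/dL was meant turns that patient away, although the patient meets the printed criterion. Neither site could show that its reading is the intended one.

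**Working it through.** **Inputs**
- Printed limit: 2.5 mg/dL (Table 6, albumin row).
- Hemoglobin limit: 9 g/dL or 5.6 mmol/L (Table 6).
- Range of measured serum albumin: not in the protocol. Assumed to be 1 to 5 g/dL.

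**Step 1. Is the table otherwise sound in its units?** The hemoglobin row states its limit twice, so it can be checked. Taking 16.114 g/mmol for the hemoglobin monomer (an assumption, not a protocol figure), 9 g/dL × 10 / 16.114 = 5.59 mmol/L, which rounds to the printed 5.6. The hemoglobin row is therefore consistent. The albumin row has no second unit to check against.

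**Step 2. Convert the printed albumin limit.** 2.5 mg/dL / 1,000 = 0.0025 g/dL, or 0.025 g/L.

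**Step 3. Compare with the assumed range.** The multiple of the limit is albumin (g/dL) × 1,000 / 2.5.

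| Albumin, g/dL | In mg/dL | Multiple of printed limit | Meets printed limit | Would meet 2.5 if read in g/dL |
|---|---|---|---|---|
| 1.0 | 1,000 | 400 | yes | no |
| 1.5 | 1,500 | 600 | yes | no |
| 2.0 | 2,000 | 800 | yes | no |
| 2.5 | 2,500 | 1,000 | yes | yes |
| 3.5 | 3,500 | 1,400 | yes | yes |
| 5.0 | 5,000 | 2,000 | yes | yes |

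The last column is there only to show where two sites could disagree. It does not assert that g/dL was intended. The two readings differ by a factor of 2,500 / 2.5 = 1,000.

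**Step 4. How much does the assumed range matter?** Very little. Even at 0.1 g/dL, a tenth of the low end assumed here, the multiple is 100 / 2.5 = 40. A patient would fail only below 0.0025 g/dL.

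**Step 5. Is it corrected elsewhere?** No. Table 15 gives no unit and Section 5.4 gives no albumin limit.

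**The case against.** The strongest reply is that this is a one-cell unit slip that most sites would recognize. Laboratory results go to the coordinating center with the checklist, eligibility questions can be referred to the study PI, and exclusion 12 lets an investigator refuse a patient with a worrying laboratory value. This lowers the practical harm and it stands to that extent. It does not remove the defect: exclusion 12 is discretionary and has no number, and the coordinating center would be checking results against a written limit that is always met.

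Three stronger readings are tempting, and the protocol does not support them.

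- A reader might infer that the organ-function criterion as a whole excludes no one. It does exclude patients: neutrophils, platelets, hemoglobin, creatinine or clearance, bilirubin, AST/ALT, INR/PT and aPTT all keep limits that can be failed.
- A reader might infer from Section 4.3.2 that low albumin raises free pralatrexate and so toxicity. That section gives binding percentages and judges displacement interactions unlikely; it does not link albumin level to free drug or to DLTs. The link is an inference, and it could concern only Arms A and B, since Arm C has no pralatrexate.
- A reader might go on to infer extra DLTs and a shifted MTD. In cohorts of one, a single DLT from any cause can move the recommended dose. That is a property of the design and does not measure the effect of this error. The protocol gives no basis for estimating how many low-albumin patients would enter or how many DLTs they would have.

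**Conclusion.** The point holds for the albumin row alone. As printed, the limit is 0.0025 g/dL, and on the assumption that measured albumin is of the order of 1 to 5 g/dL, every patient passes it by a factor of 400 to 2,000. The row therefore has no screening effect, and sites that silently change the unit will apply a different rule from sites that follow the text.

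The number of patients affected cannot be estimated from the protocol and is probably small. No sample size, confidence interval, DLT definition, dose-allocation rule or stopping bound uses this value. It is nevertheless an error in an operative eligibility rule and should be corrected. The slip looks like one of units, but the protocol does not state the intended value, so the correct number and unit are for the sponsor to confirm.

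**What to change.** The sponsor should confirm the intended albumin number and unit, then correct the albumin cell of Table 6 so that it is on a scale the laboratories report and a measured value can fail. Because the study is international, giving the limit in both g/dL and g/L would remove any doubt, much as the hemoglobin row already gives two units. The eligibility checklist is not among the documents; check that it matches the corrected cell.

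The cost is one table cell, a checklist check and a line in the summary of changes. A few patients with very low albumin may become ineligible. The correction is still useful because Section 10.4 plans further accrual: up to 5 more participants in Arm A, 6 in Arm C and 26 in Arm B.

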### 6.1.2 Subject Exclusion Criteria

The subject must be excluded from participating in the trial if the subject:

- Has lack of resolution of adverse events (AE) due to previously administered antineoplastic therapy to grade 1 or less according to National Cancer Institute (NCI) Common Terminology Criteria for Adverse Events (CTCAE), version 5.0
- Had prior therapy with PD-1 inhibitors.

3. Has a diagnosis of immunodeficiency or has been receiving any immunosuppressive therapy within 7 days prior to the first dose of trial treatment. Use of steroid equivalent to prednisone 10 mg/day does not constitute an exclusion criterion.
4. Has a known history of active TB (Bacillus Tuberculosis)
5. Hypersensitivity to pralatrexate, or decitabine or pembrolizumab or any of its excipients.
6. Has received prior allogeneic stem cell transplant.
7. Has a known additional malignancy that is progressing or requires active treatment. Exceptions include basal cell carcinoma of the skin or squamous cell carcinoma of the skin that has undergone potentially curative therapy or *in situ* cervical cancer.
8. Has known active central nervous system (CNS) metastases and/or carcinomatous meningitis. Subjects with previously treated brain metastases may participate provided they are stable (without evidence of progression by imaging for at least four weeks prior to the first dose of trial treatment and any neurologic symptoms have returned to baseline), have no evidence of new or enlarging brain metastases, and are not using steroids for at least 7 days prior to trial treatment. This exception does not include carcinomatous meningitis which is excluded regardless of clinical stability.
9. Has active autoimmune disease that has required systemic treatment in the past 2 years (i.e. with use of disease modifying agents, corticosteroids or immunosuppressive drugs). Replacement therapy (e.g. thyroxine, insulin, or physiologic corticosteroid replacement therapy for adrenal or pituitary insufficiency, etc.) is not considered a form of systemic treatment. The following are exceptions to this criterion: subjects with vitiligo or alopecia; subjects with hypothyroidism (e.g., following Hashimoto syndrome) stable on hormone replacement; subjects with psoriasis not requiring systemic treatment; patients with autoimmune phenomena secondary to active lymphoma.
10. Has known history of, or any evidence of non-infectious pneumonitis/interstitial lung disease that required steroids or has current pneumonitis/interstitial lung disease.
11. Has an active infection requiring systemic therapy.
12. Has a history or current evidence of any condition, therapy, or laboratory abnormality that might confound the results of the trial, interfere with the subject's participation for the full duration of the trial, or is not in the best interest of the subject to participate, in the opinion of the treating investigator.
13. Has known psychiatric or substance abuse disorders that would interfere with cooperation with the requirements of the trial.
14. Is pregnant or breastfeeding or expecting to conceive or father children within the projected duration of the trial, starting with the pre-screening or screening visit through 120 days after the last dose of trial treatment.
15. Has received prior therapy with an anti-PD-1, anti-PD-L1, or anti-PD-L2 agent.
16. Has a known history of Human Immunodeficiency Virus (HIV) (HIV 1/2 antibodies).
17. Has known active Hepatitis B (e.g., HBsAg reactive) or Hepatitis C (e.g., HCV RNA [qualitative] is detected).
18. Has received a live vaccine or live-attenuated vaccine within 30 days of planned start of study therapy. Administration of killed vaccines is allowed.

*Note: Seasonal influenza vaccines for injection are generally inactivated flu vaccines and are allowed; however intranasal influenza vaccines (e.g., Flu-Mist®) are live attenuated vaccines, and are not allowed.*

## 6.2 Trial Treatments

The treatment arms to be used in this trial are outlined in Table 7, Table 8 and Table 9 below.

Table 7: Trial Treatment – Arm A

Agent	Premedication Precautions	Dose	Route	Schedule A	Cycle Length
Pembrolizumab	N/A	200 mg (flat dose)	IV Administered first during cycle 1	Days 1*	Q3W
Pralatrexate	B12 and Folate supplementation (to be started within one week before initiation of treatment), and leucovorin (LV) as outlined	20 or 30 mg/m  **	IV push	Days 1, 8, 15	Q4W

\*Day 1 for pembrolizumab administration refers only to cycle 1 of treatment. Pembrolizumab will be continued every 3 weeks following the first administration.

\*\* Doses as appropriate for assigned dose level. Pralatrexate dose will be calculated using weight at cycle 1 day 1, unless weight has changed more than 10%. If so, the total dose should be calculated on the updated weight.

Table 8: Trial Treatment – Arm B

Agent	Premedication Precautions	Dose	Route	Schedule B	Cycle Length
Decitabine	Antiemetic	10 mg/m  *	IV	Days 1, 2,3,4,5	Q4W
Pralatrexate	B12 and Folate supplementation (to be started within one week before initiation of treatment) and leucovorin (LV)	20 mg/m  *	IV push	Days 1,8,15	
Pembrolizumab	N/A	200 mg (Flat dose)	IV	Day 8**	Q3W

\* Doses as appropriate for assigned dose level. Pralatrexate and decitabine dose will be calculated using weight at cycle 1 day 1, unless weight has changed more than 10%. If so, the total dose should be calculated on the updated weight.

\*\*Day 8 for pembrolizumab administration refers only to cycle 1 of treatment. Pembrolizumab will be continued every 3 weeks following the first administration.

Table 9: Trial Treatment – Arm C

Agent	Premedication Precautions	Dose	Route	Schedule C	Cycle Length
Pembrolizumab	N/A	200 mg (flat dose)	IV (Administered first during cycle 1)	Days 8*	Q3W
Decitabine	Antiemetic	20 mg/m  **	IV	Days 1,2, 3, 4, 5	Q4W

*\*Day 8 for pembrolizumab administration refer only to cycle 1 of treatment. Pembrolizumab will be continued every 3 weeks following the first administration.*

*\*\*Doses as appropriate for assigned dose level. Decitabine dose will be calculated using weight at cycle 1 day 1, unless weight has changed more than 10%. If so, the total dose should be calculated on the updated weight.*

All patients receiving pralatrexate will receive folic acid at the dose of 1,000 mg orally daily and vitamin B12 intramuscularly every 2 cycles (8 weeks) as recommended in the package insert of the product. The vitamin supplementation will start prior to the first dose of pralatrexate as recommended in the drug package insert. If leucovorin is being used for rescue, this should be used at the dose of 15 mg orally twice daily and should be held the day before, of and after pralatrexate.

Trial treatment should begin on the day of randomization or as close as possible to the date on which treatment is allocated/assigned.

## 7.0 DOSE SELECTION/DELAYS/MODIFICATION

### 7.1 Dose Selection

The rationale for selection of doses to be used in this trial is provided in Section 4.0– Background and Rationale.

### 7.2 Dose Delays

These dose delays apply to all drugs and patients on all study arms. Additional delays may apply for specific drugs (see sections 7.3.1 and 7.3.2 below).

- Study drugs can be administered within 48 hours of their scheduled time.
- Study drugs will be held for DLT and any grade 3/4 toxicity not addressed in [section 5.3](#) until the AE returns to grade  $\leq 2$  unless otherwise specified in the sections below.
- If the interruption lasts for more than 14 days, study treatment will be discontinued.

### 7.3 Dose Modification

If the administration of a study drug combination (Arm A, Arm B, or Arm C) leads to a toxicity beyond cycle 1 at a given dose level, dose modifications may occur in accordance with the drug FDA approved package insert, or as outlined in the dose de-escalation tables. This post-cycle 1 DLT will not count towards the overall determination of MTD for this study.

#### 7.3.1 Immune Related Adverse Events

Adverse events (both non-serious and serious) associated with pembrolizumab exposure, including coadministration with additional compounds, may represent an immunologic etiology. These adverse events may occur shortly after the first dose or several months after the last dose of pembrolizumab/combination treatment and may affect more than one body system simultaneously. Therefore, early recognition and initiation of treatment is critical to reduce complications. Based on

existing clinical study data, most irAEs were reversible and could be managed with interruptions of pembrolizumab/combination treatment, administration of corticosteroids and/or other supportive care. For suspected irAEs, ensure adequate evaluation to confirm etiology or exclude other causes. Additional procedures or tests such as bronchoscopy, endoscopy, skin biopsy may be included as part of the evaluation. Dose modification and toxicity management guidelines for irAEs associated with pembrolizumab/combination treatment are provided in Table 10 below. See [Section 7.8](#) for supportive care guidelines, including use of corticosteroids.

#### **Attribution of Toxicity:**

When study interventions are administered in combination, attribution of an adverse event to a single component is likely to be difficult. Therefore, while the investigator may attribute a toxicity event to the assigned treatment combination, to pralatrexate alone (Arm A or B), to decitabine alone (Arm B or C) or to pembrolizumab alone, for adverse events listed in Table 10, both (all, for Arm B) interventions must be held according to the criteria in Table 10 Dose Modification and Toxicity Management Guidelines for Immune-Related Adverse Events.

